3.3.3 Definition of Maximum Tolerated Dose

The MTD is defined as the highest dose at which at least six subjects complete the treatment course with no more than one subject experiencing a DLT. If two or more subjects experience a DLT at a given dose level, the MTD will have been exceeded and no additional subjects will be treated at that level. The DSMB will convene to examine the data and review the drug-relatedness of the relevant toxicities in light of the typically complex course and safety experience of HSCT patients. If the DSMB agrees that the relevant toxicities were drug-related and met the other criteria for DLT, no further dose escalation will occur and, depending on the nature of the DLTs, the study may be stopped. Throughout the study, the Sponsor will report any significant findings by the DSMB to the FDA.

3.3.4 Dose Escalation Plan

Subjects will be enrolled sequentially according to the dose escalation diagram shown in Figure 4. If a DLT occurs in any subject, it must be treated, if necessary, and monitored until it stabilizes or recovers to no worse than CTC grade 2 toxicity (grade 1 if reported toxicity is initially grade 2) prior to additional enrollment. Subjects will be monitored for toxicity with assessments listed in Appendix 1 (Schedule of Assessments).

To minimize the chance of simultaneous graft failures possibly due to exposure to opebacan, only two subjects may be simultaneously enrolled in any dose group until one of them successfully engrafts, defined as ANC $\geq 500/\mu L$ for three consecutive days, with the first day (the day of engraftment) occurring no later than Day 28. Once engraftment occurs in one of the first two subjects in a dose group, the third subject may be enrolled. When engraftment occurs in a second subject within a dose group, the fourth subject may be enrolled, and when

engraftment occurs in a third subject in a dose group, the fifth subject may be enrolled. Finally, when engraftment occurs in a fourth subject in a dose group, the sixth subject may be enrolled.

After all subjects in a dose group have completed study procedures through Day 28, all available safety information will be reviewed by the DSMB. Dosing may begin for the next dose group at the next higher dose level if no more than one subject in the previous group has experienced a DLT and, in the opinion of the DSMB, there are no clinically significant safety concerns at the previous dose level. If, in the opinion of the DSMB, there are clinically significant safety concerns, the DSMB may recommend that the study be discontinued.

If graft failure occurs in any dose group, that dose group will be expanded to 12 subjects. If a second graft failure occurs in the expanded cohort, the DSMB will determine if the study should be stopped after looking at the data for the two subjects whose grafts failed. As with other dose groups, enrollment in the expanded cohort will be staggered to minimize the chance of multiple graft failures. Only two subjects may be simultaneously enrolled until one of them successfully engrafts, at which time an additional subject may be enrolled.

Enroll 6 subjects in dose group 1 DLT in no more than DLT in > 1/6 subjects: 1/6 subjects: Hold enrollment and Go to dose group 2 convene DSMB Enroll 6 subjects in dose group 2 DLT in > 1/6 subjects: DLT in no more than 1/6 subjects: Hold enrollment and Go to dose group 3 convene DSMB Enroll 6 subjects in dose group 3 DLT in no more than DLT in > 1/6 subjects: Hold enrollment and 1/6 subjects: Go to dose group 4 convene DSMB Enroll 6 subjects in dose group 4 DLT in > 1/6 subjects: DLT in no more than

Figure 4
Dose Escalation Diagram

Note: To minimize the chance of simultaneous graft failures possibly due to exposure to opebacan, only two subjects may be simultaneously enrolled in any dose group until one of them successfully engrafts, defined as ANC ≥ 500/µL for three consecutive days, with the first day (the day of engraftment) occurring no later than Day 28. If a subject experiences graft failure, the subject's cohort will be expanded to 12 subjects. If a second graft failure occurs in the expanded cohort, the DSMB will determine whether the study should be stopped after reviewing all available information on the two subjects whose grafts failed.

Hold enrollment and

convene DSMB

1/6 subjects:

Go to dose group 5

Enroll 6 subjects in dose group 5

Table 2 shows the probability of dose escalating assuming different DLT incidence rates. The calculations of these probabilities are based on binomial distributions.

Table 2
Probabilities of Dose Escalating Assuming
Different DLT Incidence Rates

Assumed DLT Incidence Rate ¹	Probability of Dose Escalating (DLT in ≤ 1 Subject) ²
.02 (2%)	.9943
.04 (4%)	.9784
.07 (7%)	.9392
.10 (10%)	.8857
.20 (20%)	.6554
.30 (30%)	.4202
.40 (40%)	.2333
.50 (50%)	.1094

The assumed DLT incidence rate is the assumed probability of any single subject experiencing a DLT.

3.4 Selection of Study Population

Screening for eligibility will proceed in two parts. The first, a prescreen, will establish potential eligibility for treatment while a second, a final screen, will be used to determine whether drug administration will be initiated. Prescreening assessments must be performed within 30 days of admission to the hospital for the conditioning regimen and subsequent HSCT procedure. The final screen must occur on Day –1. If the final screening criteria are met, treatment with opebacan will begin on Day –1, 18 to 36 hours prior to the infusion of donor cells on Day 0.

This protocol is designed for patients undergoing non-T cell depleted myeloablative HSCT. Thus, T cell depletion regimens, including those using Campath or ATG either pre- or post-transplant, are not permitted, and those who have received such regimens are not eligible for enrollment.

3.4.1 Prescreen Eligibility Criteria

3.4.1.1 Prescreen Inclusion Criteria

Subjects may be included in the study if they meet all of the following criteria:

• Subject has been informed about the study and signed a XOMA/IRB-approved informed consent prior to performance of any study-related procedures

² The probability of dose escalating is the probability of ≤ 1 of the 6 subjects in a cohort experiencing a DLT.

• Subject consents to an IV catheter inserted and maintained for the purpose of opebacan administration

- Age \geq 18 and \leq 60, and undergoing allogeneic HSCT
- Life expectancy ≥ 8 weeks
- Scheduled for treatment with a conditioning regimen intended to be myeloablative, defined as containing one of the following:
 - Busulfan at ≥ 14 mg/kg PO (or IV equivalent)
 - TBI \geq 1000 cGy
 - Melphalan 180 mg/M² (or per kg equivalent)

(Note: Subjects with Fanconi anemia who are undergoing matched sibling transplant with any radiation or busulfan (IV or PO) regimen are eligible regardless of dose intensity.)

- Meets the following standard performance and end-organ function criteria for stem cell transplantation:
 - Pulmonary function: Room air O₂ saturation > 95% and no clinical evidence of pulmonary insufficiency
 - Renal function: Serum creatinine must be < 1.5× the upper limit of normal for age or, if serum creatinine is elevated beyond normal for age, must have creatinine clearance or GFR > 50% of lower limit of normal for age.
 - Liver function: AST and ALT ≤ 3 times the upper limit of normal for age and total serum bilirubin ≤ 1.5 times the upper limit of normal for age. (Note: In the presence of documented intravascular hemolysis, the direct bilirubin component must be less than $2\times$ the upper limit of normal for age.)
 - \geq 80% performance score on the Karnofsky Scale; see Appendix 3)
 - Cardiac function: Adequate cardiac function by clinical assessment, normal shortening fraction or ejection fraction for age, and normal cardiac troponin T level (< 0.1 ng/mL)
- Female subjects of child-bearing age must have a negative urine or serum pregnancy test. Sexually active male and female subjects of reproductive age must be using a form of contraception considered effective and medically acceptable by the Investigator.

3.4.1.2 Prescreen Exclusion Criteria

Subjects will be excluded from the study if they meet **any** of the following criteria:

• Treatment with T cell depletion regimens, including those using Campath or ATG, either pre- or post-transplant

• Cumulative lifetime exposure of > 300 mg/M² of anthracycline (expressed as doxorubicin equivalent dose)

- Active infection. Freedom from active infection is defined as the absence of an infectious diagnosis or (in subjects who have had a recent positive infectious diagnosis) the resolution of fever plus documentation of negative cultures or antigen testing, continuation or completion of a course of appropriate therapy, and the presence of stable to resolving clinical symptoms and/or radiographic signs. The Investigator must document the subject's infectious disease status in the chart prior to enrolling the subject in the study.
- Prophylactic antibacterial antibiotics beyond standard institutional practice.
 Subjects whose individual risk of infection is so great as to necessitate additional prophylactic administration of systemic antibiotics are excluded. If a subject does not require prophylaxis but the Investigator believes prophylaxis may be advisable, the Investigator should contact the XOMA Medical Monitor before enrolling the subject. Use of gut decontamination is permitted if it is standard institutional practice.
- Positive for HIV
- Any prior stem cell transplant
- Prior history of CHF
- Projected need for heparin anticoagulation during the study medication infusion period. Use of dextran sulfate is also prohibited during the infusion period.
- Enrollment on a chemotherapy regimen where conditioning extends beyond Day
 1
- Enrollment on a regimen where it will not be possible to achieve an 18 to 36 hour window between initiation of opebacan and infusion of donor cells.
- Cord blood is the source of a subject's transplanted cells.

3.4.2 Final Pretreatment Eligibility Criteria

3.4.2.1 Final Pretreatment Inclusion Criteria

Subjects may be included in the study if **all** of the following occurs:

- 1. The Principal Investigator or designee has reviewed and approved subject eligibility for the HSCT prior to proceeding with opebacan administration and confirmed that the interval between initiating opebacan and administering donor cells will be between 18 and 36 hours.
- 2. All Day –1 pre-dose assessments described in Appendix 1 have been performed. Results for some of these assessments may not be available prior to proceeding with opebacan administration.

3.4.2.2 Final Pretreatment Exclusion Criteria

Subjects will be excluded from the study upon re-evaluation at Day -1 if they have evidence of CTC Grade 4 toxicity, including but not limited to any of the following:

- Active infection
- Dialysis dependence
- Need for continuous venovenous hemofiltration
- Requirement for mechanical ventilation
- Veno-occlusive disease
- Requirement for pressor support
- Presence of disseminated intravascular coagulation

3.5 Enrollment

Once prescreening is completed and subject eligibility is confirmed, a subject will be assigned a subject number by the Sponsor. Donors who sign an informed consent will be assigned a tracking number that can be used for tracking donor samples and will link those samples with the subject who received the donor's stem cells.

Sites must contact the following individual for subject number assignment:

[name] [contact]

[contact]

Eligible subjects will be assigned to one of five successive dose groups of six subjects each (see Section 3.1 and Table 1). Enrolled subjects who discontinue the trial prior to receiving opebacan will be replaced. Subjects will also be replaced if they do not receive at least 80% of their scheduled dose of opebacan and/or do not complete assessments for at least 7 days following the end of their opebacan infusion.

3.6 Treatment

3.6.1 Formulation

Opebacan is supplied as a clear, colorless, sterile non-pyrogenic solution in 10 mL single use glass vials at a concentration of 2 mg/mL in 5 mM sodium citrate/0.15 M sodium chloride buffer, pH 5.0 with 0.2% poloxamer 188 and 0.002% polysorbate 80, containing no preservative.

For further details, see the Investigator's Brochure.

3.6.2 Labeling

All vial labels will include the information specified in Table 3.

Table 3
Required Label Information

Logo of manufacturer:	XOMA
Protocol number:	BPSC030
Subject number:	[TBD]
Name of study drug:	opebacan, rBPI ₂₁ , NEUPREX [®]
Instructions:	Sterile solution for intravenous use. See clinical protocol for dosage and administration.
Part number:	12580
Contents:	10 mL (2 mg/mL)
Lot number:	[TBD]
Storage instructions:	Store at 2-8°C (36-46°F)
Caution:	New Drug — Limited by Federal Law to Investigational Use
Manufactured by:	XOMA (US) LLC, Berkeley, CA 94710

3.6.3 Shipping

A sufficient number of vials of opebacan for all doses for each subject will be shipped to the study site. Each vial will contain 10 mL of opebacan.

If the packaging is damaged upon receipt or if there is anything unusual about the appearance or attributes of this study drug, the drug should not be used and the problem should be immediately reported to the following individual by phone:

[name] Manager, Clinical Operations and Data Management XOMA (US) LLC [contact]

3.6.4 Warnings

Humans administered foreign proteins are at risk of developing allergic reactions including anaphylaxis. When an anaphylactoid reaction is suspected, opebacan should be discontinued immediately and appropriate therapy (including oxygen, epinephrine, diphenhydramine, corticosteroids, and volume expansion) should be administered as medically indicated.

Subjects must not receive heparin anticoagulation during the study medication infusion period.

The study drug should be used only by physicians who are qualified by training and experience in the safe use and handling of investigational drugs. Do not use if the solution is turbid or contains particulate matter. No long-term animal studies have been performed with opebacan to determine carcinogenic potential or impairment of fertility in males or females.

3.6.5 Dosage, Administration, and Storage

3.6.5.1 *Dosage*

All subjects will receive an initial 4 mg/kg continuous IV infusion for 30 minutes. This will be followed immediately by a continuous infusion that varies, according to the dose group, in dose level and duration (see Table 1). Subjects whose conditioning regimen includes TBI will have their opebacan infusion interrupted for 1-hour TBI treatments once on Day –1 and twice on Day 0 prior to the HSCT procedure, which will take place after the opebacan infusion has been restarted for at least 2 hours.

3.6.5.2 Administration

The study drug (opebacan) should be brought to room temperature prior to infusion. Further details of administration are included in the drug administration information sheet. Throughout the dosing procedure, aseptic technique for intravenous administration should be followed. The study drug will be administered by intravenous infusion into a central or peripheral vein. Suitability of intravenous access will be determined by easy withdrawal of blood from the access, as well as easy infusion of intravenous fluids without infiltration.

The study medication must be the sole agent administered in the chosen port during the course of the infusion protocol. The venous access port will not be heparinized, but may be flushed as necessary with physiologic saline for injection. Any sign of a reaction at a site of infusion should be recorded on the subject's CRF and source document as an adverse experience. If the infusion is interrupted, it should be resumed as soon as possible. However, if more than two hours has elapsed, call XOMA's Medical Monitor at [contact] before restarting the infusion. Any unexpected attributes or appearance of the investigational drug should be reported to XOMA immediately.

3.6.5.3 Storage and Handling

All study drug must be stored refrigerated at 2-8°C (35.6-46.4°F). The study drug should not be allowed to freeze, should not be shaken, and should be stored upright.

The contents of the vials supplied are sterile and pyrogen free. Aseptic techniques must be used during withdrawal, preparation and administration. Vials contain no preservative and are for single use only.

3.6.6 Prior and Concomitant Therapy

3.6.6.1 Excluded Concomitant Medications

Subjects may not participate in any other investigational drug or device study or receive other phase I agents from the signing of the informed consent form through Day 100. If a subject has a clinical indication for emergent use of any phase I agent, the Principal Investigator at the specific site must be informed and decide with the Sponsor if the subject should be removed from the study. Consistent with good clinical care, non-standard therapies should be avoided during the study period.

Subjects must not receive heparin anticoagulation during the study medication infusion period. Use of dextran sulfate is also prohibited during the infusion period. Subjects who are receiving heparin for routine line care (e.g., a heparin lock or an intermittent small volume bolus) are eligible to receive treatment.

3.6.6.2 Allowed Concomitant Medications

Subjects undergoing HSCT receive a broad range of medications to treat the side effects of the conditioning regimen and transplant, as well as the underlying disease. All concomitant medications used during the study must be recorded on the appropriate page of the CRF. The following list of drug classes encompasses many of the concomitant medications Investigators will administer to subjects and which are acceptable for use during this trial:

- Antihypertensives
- Antibiotics
- Antivirals
- Antifungals
- IVIG
- Blood products
- Hematologic growth factors
- Antacids
- Immunosuppressives
- Phenothiazines
- Antiemetics
- Analgesics
- Electrolyte and mineral supplements
- Nutritional Support

3.7 Supportive Care Guidelines

The following supportive care guidelines must be observed:

 Subjects who are CMV seropositive and/or have seropositive donors must be monitored for CMV weekly using institutional guidelines for assay choice until Day 100. Subjects should be treated for ANY positive antigen or PCR result per institutional practice.

- Subjects must receive pre-emptive PCP treatment during the conditioning regimen according to institutional practice and reinitiate PCP prophylaxis after hematologic recovery. The total duration of PCP prophylaxis will be determined by institutional practice but it should be continued for at least 100 days after transplant. Therapy may be modified for drug intolerance.
- All subjects must receive prophylactic antifungal therapy during transplant. Choice of agents is per institutional practice.
- Any use of hematopoietic growth factors must be recorded in the study documentation. All blood products should be irradiated and administered per institutional practice.
- General support of fluids, electrolytes, nutrition and other medical needs should be per institutional guidelines.
- Subjects must not use heparin anticoagulation during the study medication infusion period. Use of dextran sulfate is also prohibited during the infusion period.
- The study medication must be the sole agent administered in the chosen port during the course of the infusion protocol.

3.8 Outcome Measures

3.8.1 Biological and Clinical Activity

Biological and clinical activity will be assessed through an evaluation of the following outcome measures:

- Time to engraftment, defined as the first of three consecutive daily measurements of ANC $\geq 500/\mu L$
- Inflammatory markers (such as LPS, LBP, IL-6, CRP and other exploratory biomarkers)
- Inflammatory states such as presence of fever and infection
- Transplant-related complications including, but not limited to, aGvHD, inadequate oral intake, presence of oral mucositis, veno-occlusive disease of the liver, and idiopathic pneumonitis.

3.8.2 Safety Outcome Measures

Safety will be assessed by pre- and post-treatment serial measurements of vital signs and clinical laboratory assessments and by the recording of adverse clinical events with an emphasis on infectious and non-infectious regimen-related toxicities.

3.8.3 Pharmacokinetic Assessment and Sampling Schedule

The pharmacokinetics of opebacan will be determined from samples collected from each subject at the time points shown in Appendix 2. Note that the timing of PK sampling varies by dosing group. The timing of PK draws for the various dose groups and the acceptable windows for those draws are as follows:

- Subjects in Dose Groups 1, 2, and 3 will receive 3-day opebacan infusions and will have PK samples collected at prescreening (to measure the level of endogenous BPI), on Day –1 (predose and 30 [± 5 minutes], 45 [± 5 minutes], 90 [± 15 minutes], and 270 [± 30 minutes] minutes following the start of infusion), Day 0 (24 hours [± 60 minutes] following the start of infusion), Day 1 (48 hours [± 60 minutes] following the start of infusion), Day 2 (within 1 hour prior to and 15 [± 5 minutes], 30 [± 5 minutes], 60 [± 10 minutes], and 240 [± 30 minutes] minutes following the end of infusion), Day 3 (24 hours [± 60 minutes] following the end of infusion), and Day 100.
- **Subjects in Dose Group 4** will receive 7-day opebacan infusions and will have PK samples collected at prescreening (to measure the level of endogenous BPI), on Day -1 (predose and 30 [± 5 minutes], 45 [± 5 minutes], 90 [± 15 minutes], and 270 [± 30 minutes] minutes following the start of infusion), Day 0, Day 1, Day 6 (within 1 hour prior to and 15 [± 5 minutes], 30 [± 5 minutes], 60 [± 10 minutes], and 240 [± 30 minutes] minutes following the end of infusion), Day 7 (24 hours [± 60 minutes] following the end of infusion), and Day 100.
- **Subjects in Dose Group 5** will receive 14-day opebacan infusions and will have PK samples collected at prescreening (to measure the level of endogenous BPI), on Day -1 (predose and 30 [± 5 minutes], 45 [± 5 minutes], 90 [± 15 minutes], and 270 [± 30 minutes] minutes following the start of infusion), Day 0, Day 1, Day 6, Day 10, Day 13 (within 1 hour prior to and 15 [± 5 minutes], 30 [± 5 minutes], 60 [± 10 minutes], and 240 [± 30 minutes] minutes following the end of infusion), Day 14 (24 hours [± 60 minutes] following the end of infusion), and Day 100.

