3.0 STUDY DESIGN

3.1 Description of the Study

This is a phase I/II, open-label, dose- and duration-escalation study of the safety and PK of opebacan in subjects undergoing non-T cell depleted myeloablative HSCT from an allogeneic donor. Subjects who sign an informed consent and pass initial screening prior to the start of their HSCT conditioning regimen will be re-evaluated on Day -1. Subjects who meet the eligibility criteria for HSCT at final screening will begin their IV infusions of opebacan on Day -1. Subjects whose conditioning regimen consists of chemotherapy only will receive a continuous opebacan infusion following completion of chemotherapy treatment on Day -1. Subjects whose conditioning regimen includes total body irradiation (TBI) will have three 1-hour interruptions in their opebacan infusions (one on Day -1 and two on Day 0) to accommodate TBI treatment. Following the final interruption on Day 0, the infusion must be restarted at least 2 hours prior to the HSCT.

The HSCT procedure will take place on Day 0, between 18 and 36 hours following the start of opebacan treatment, and approximately 4 to 12 days following initiation of the conditioning regimen.

Eligible subjects will be assigned to one of five successive dose groups of six subjects each. Subjects in successive dose groups will be treated with opebacan at escalating doses and durations as shown in Table 1.

[figure not shown]
Table 1
Study BPSC030 Dose Groups

[figure not shown]
Dose Group	No. of Subjects	Dose Regimen	Total Dose
1	6	4 mg/kg continuous IV infusion for 30 minutes followed immediately by 6 mg/kg/day continuous IV infusion for 3 days	22 mg/kg
2	6	4 mg/kg continuous IV infusion for 30 minutes followed immediately by 9 mg/kg/day continuous IV infusion for 3 days	31 mg/kg
3	6	4 mg/kg continuous IV infusion for 30 minutes followed immediately by 12 mg/kg/day continuous IV infusion for 3 days	40 mg/kg
4	6	4 mg/kg continuous IV infusion for 30 minutes followed immediately by 12 mg/kg/day continuous IV infusion for 7 days	88 mg/kg
5	6	4 mg/kg continuous IV infusion for 30 minutes followed immediately by 12 mg/kg/day continuous IV infusion for 14 days	172 mg/kg

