6.7 Pharmacokinetic, Pharmacodynamic, and Other Analyses

Non-compartmental pharmacokinetic analysis will be performed on the data. The following pharmacokinetic parameters will be obtained: peak concentration after the 30 minute dose, steady state concentration during long-term infusion, endogenous BPI levels measured at predose and 24 hours after the end of the last infusion, and opebacan clearance.

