Appendix 2: Study BPSC030 PK Sampling Schedule¹

Study Day	sscreen			-1			0	1			2			3			6			7	10			13			14	100
Minutes ²	Pre	Pre	30	45	90	270	1440	2880	EOI	15	30	60	240	1440	EOI	15	30	60	240	1440		EOI	15	30	60	240	1440	
Group 1	X^3	X^3	X	X	X	X	X	X	X	X	X	X	X	X														X
Group 2	X^3	X^3	X	X	X	X	X	X	X	X	X	X	X	X														X
Group 3	X^3	X^3	X	X	X	X	X	X	X	X	X	X	X	X														X
Group 4	X^3	X^3	X	X	X	X	X	X							X	X	X	X	X	X								X
Group 5	X^3	X^3	X	X	X	X	X	X							X^4						X	X	X	X	X	X	X	X
Donor	X^3																											

¹ PK sample must be drawn from a different vein than that used for opebacan administration.

For Days –1, 0, and 1, sampling time is shown in minutes following initiation of opebacan treatment. For Days 2 and 3 (Groups 1, 2, and 3), Days 6 and 7 (Group 4), and Days 13 and 14 (Group 5), sampling times are shown in minutes following the end of infusion (EOI). The "EOI" sample must be drawn within one hour prior to the end of the opebacan infusion. The acceptable windows for the other PK draws are as follows: 15 ± 5 minutes, 30 ± 5 minutes, 45 ± 5 minutes, 60 ± 10 minutes, 90 ± 15 minutes, 240 ± 30 minutes, 270 ± 30 minutes, 1440 ± 60 minutes, and 2880 ± 60 minutes.

³ The PK samples for the donor and subject at prescreen and for the subject at predose on Day –1 are used for measuring the level of endogenous BPI.

The PK sample for Group 5 subjects on Day 6 is drawn along with other blood draws on that day. Though it appears in the EOI column, the infusion for this dose group does not end until Day 13.

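### The sample meant to catch the loading-dose peak may be drawn up to 5 minutes after the infusion rate falls 16- to 32-fold, and will then understate the peak

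*Supplement*

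**What the plan says.** Section 3.6.5.1 gives every dose group the same load: "All subjects will receive an initial 4 mg/kg continuous IV infusion for 30 minutes". Table 1 in section 3.1 sets what follows at once. For Group 1 it is "4 mg/kg continuous IV infusion for 30 minutes followed immediately by 6 mg/kg/day continuous IV infusion for 3 days"; the continuous rate is 9 mg/kg/day in Group 2 and 12 mg/kg/day in Groups 3 to 5.

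Section 3.8.3 places the Day –1 samples at "30 [± 5 minutes], 45 [± 5 minutes], 90 [± 15 minutes" after the start of infusion, with a further sample at 270 minutes. Appendix 2 repeats the two-sided window: "15 ± 5 minutes, 30 ± 5 minutes, 45 ± 5 minutes". Section 6.7 lists "peak concentration after the 30 minute dose" among the parameters to be obtained by non-compartmental analysis.

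At the end of the long infusion the plan uses a one-sided rule. In Appendix 2, the end-of-infusion "sample must be drawn within one hour prior to the end of the opebacan infusion". Nothing in the protocol applies the same rule to the 30-minute sample.

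**The concern.** The nominal time of the peak sample coincides with the moment the rate drops. Up to 30 minutes the plasma level is still rising or has levelled off; after 30 minutes it falls towards a much lower plateau. A window symmetric around that moment mixes the two phases.

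Non-compartmental analysis takes the peak from the observed concentrations. Recording the actual draw time would show that a sample was late, but it would not restore the value that was missed. The error runs one way: whichever side of 30 minutes the draw falls on, the reading is below the true peak, and on the late side it may be far below.

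Pharmacokinetics is the second objective (section 2.0), and section 6.2 rests the sample size mainly on PK/PD considerations. With six subjects per group, a few late draws can shift a group's peak summary.

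**Working it through.** **Check on the dose inputs.** Load plus rate × days gives 4 + 6×3 = 22, 4 + 9×3 = 31, 4 + 12×3 = 40, 4 + 12×7 = 88 and 4 + 12×14 = 172 mg/kg. These are the totals in Table 1.

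**Rate drop at 30 minutes.** The load is 4 mg/kg per 30 min × 1440 min = 192 mg/kg/day.
- Group 1: 192/6 = 32-fold
- Group 2: 192/9 = 21.3-fold
- Groups 3–5: 192/12 = 16-fold

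**Clearance implied by the protocol (rate ÷ steady-state level).**
- Section 3.2.1.1, 2 mg/kg over 24 h with 67 ng/mL: (2,000,000/1440)/67 = 20.7 mL/min/kg
- Section 3.2.1.4, 6 mg/kg/day with 250–280 ng/mL: (6,000,000/1440)/250 = 16.7 and /280 = 14.9
- Section 3.2.1.4, modelled 24 mg/kg/day for about 1000 ng/mL: (24,000,000/1440)/1000 = 16.7

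The range is about 15–21 mL/min/kg.

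**Model (assumed).** One compartment, linear, with k = CL/V. Up to 30 min, C(t) = (L/CL)(1 − e^(−kt)), with L = 4,000,000/30 = 133,333 ng/kg/min. After 30 min, C(t) = M/CL + [C(30) − M/CL]·e^(−k(t−30)), where M is the maintenance rate. V is not in the documents and is varied.

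**Worked case:** Group 1, CL = 16.67 mL/min/kg, V = 200 mL/kg.
- k = 16.67/200 = 0.0833 per min (half-life 8.3 min)
- C(30) = 8000 × (1 − e^(−2.5)) = 7343 ng/mL
- M/CL = 4167/16.67 = 250 ng/mL
- C(35) = 250 + (7343 − 250) × e^(−0.4167) = 4926 ng/mL, which is 67% of the peak (33% low)
- C(25) = 8000 × (1 − e^(−2.083)) = 7004 ng/mL, which is 95% of the peak (5% low)

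**Across CL 14.9–20.7 mL/min/kg and maintenance 6–12 mg/kg/day, shortfall against the 30-minute level:**

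| V assumed (mL/kg) | Half-life (min) | Draw at 35 min | Draw at 25 min | Mean, draws even over 25–35 min |
|---|---|---|---|---|
| 50 | 1.7–2.3 | 73–85% | 0% | 23–28% |
| 100 | 3.3–4.7 | 49–63% | 0–1% | 14–18% |
| 200 | 6.7–9.3 | 29–39% | 3–5% | 9–11% |
| 300 | 10–14 | 20–28% | 6–8% | 7–9% |
| 500 | 17–23 | 12–18% | 9–11% | 6–7% |
| 1000 | 33–47 | 6–9% | 13–14% | 5% |

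The late side of the window is the worse one up to about 500 mL/kg, where the two sides are close. At 1000 mL/kg the early side is worse.

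**The case against.** The strongest reply is that the size is unknown. Clearance alone does not fix a half-life, and the range runs from severe to slight. A reader might infer from the high clearance that decline is rapid at any plausible volume; the table does not bear that out at 500 or 1000 mL/kg. The clearance itself comes from other patient groups at 67–280 ng/mL plus one modelled level, and is carried up to a modelled peak of about 3–9 µg/mL. If clearance falls at higher levels, the late-draw error shrinks. The 35-minute draw is also the extreme case; the mean over the window is much smaller. All of this stands.

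Two further inferences are tempting and unsupported. One is that timing noise would swamp differences between subjects or groups: the documents give no variability for the peak, and every group receives the same load, so no dose-related difference in this peak is expected. The other is that the safety case depends on this measurement: section 3.2.1.4 justifies the load from animal toxicology and earlier human experience, and its 1 µg/mL ceiling is a steady-state level. The DLT and MTD rules in sections 3.3.2 and 3.3.3 do not use the peak. Section 6.8 says escalation will draw on PK data but does not name the peak.

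Finally, no separate SAP is shown, and the drug administration information sheet cited in section 3.6.5.2 is not available; handling of actual draw times may be set out there. That could cover flagging, but a correction at analysis cannot recover a peak that was not sampled, and the window itself is fixed in the protocol.

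**Conclusion.** The point holds as a sampling weakness of uncertain size. The two-sided window, the 16- to 32-fold drop at exactly 30 minutes and the listed peak parameter are all in the protocol, and no passage shown requires the draw to come before the drop. A draw after the drop understates the peak. Under the assumptions above, the worst compliant late draw is low by 6% to 85% depending on volume, and the average over evenly spread draws is about 5–28%.

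The damage is confined to one descriptive parameter. Steady-state concentration, and clearance taken as rate over steady-state level, come from other samples. The 45- and 90-minute samples describe the decline after the load and do not replace the peak. The correction is worth making because it is cheap and improves a listed parameter of a stated objective; the documents do not show that any safety decision would change.

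**What to change.** In section 3.8.3 and Appendix 2, replace the ±5 minute window on the 30-minute sample with a requirement to draw it before the rate is changed, as close to the change as practical and at most 5 minutes before. This matches the one-sided rule already used for the end-of-infusion sample. Keeping the draw close to the change matters because, if the volume is large, an early draw also reads low (13–14% at 25 minutes with 1000 mL/kg).

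Record the actual time of the rate change and of the draw. In section 6.7, state that a sample drawn after the change is flagged and that the peak summary is reported without it.

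Cost: a short edit in each place, slightly tighter bedside timing, and possibly a few peak values lost from groups of six, since section 6.6 rules out imputation. No sample is added and no dose changes.
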